### 14.2. Sample Size Calculation

This is a pivotal Phase 3, open-label, single-arm, single-dose, study assessing the efficacy and safety of AVXS-101 (gene replacement therapy) in up to twenty (20) patients with spinal muscular atrophy (SMA) Type 1 who meet enrollment criteria, may be either symptomatic or pre-symptomatic and are genetically defined by no functional survival motor neuron 1 gene (*SMN1*) with 1 or 2 copies of survival motor neuron 2 gene (*SMN2*) and who are < 6 months (< 180 days) of age **at the time** of gene replacement therapy (Day 1). Enrolling up to twenty (20) patients under the broader enrollment criteria is projected to enable enrollment of at least 15 patients that meet the Intent-to-Treat Population (ITT) criteria. The ITT population is identified as symptomatic patients with bi-allelic *SMN1* deletions and 2 copies of *SMN2* without the *SMN2* gene modifier mutation (c.859G>C) and will comprise the primary population for evaluation of the primary and secondary endpoints. Study power is based upon efficacy analysis of the ITT population. Furthermore, the first 3 patients enrolled must meet criteria for the Intent-To-Treat Population to enable a comparison of CHOP-INTEND scores at 1-month following gene replacement therapy to enable a comparison of patient response between AVXS-101-CL-303 patients and Cohort 2 patient results from the Phase 1 trial (AVXS-101-CL-101). Patients with 1 copy of *SMN2*, pre-symptomatic patients and patients with the *SMN2* gene modifier mutation (c.859G>C) and other permutations outside of those specified in the ITT population will be evaluated separately as part of additional subgroup analyses. Details of all analyses will be contained within the Statistical Analysis Plan.

The 2 co-primary efficacy endpoints will be assessed in sequence: The endpoint of functional independent sitting will be assessed first and, only if this assessment meets statistical significance will the endpoint of survival be assessed.

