#### 14.3.2. Primary and Secondary Efficacy Analysis

Primary and secondary efficacy analyses will be based on the ITT population, those patients that are symptomatic with biallelic- deletion mutations of *SMN1* and 2 copies of *SMN2* without the *SMN2* gene modifier mutation (c.859G>C). These analyses are to test the superiority of AVXS-101 to the results from natural observation study (PNCR) [21].

The first co-primary efficacy hypothesis to be tested is:

$$\begin{aligned} \mathbf{H}_0: p_{AVXS-101} &= 0.1\% \\ &\textit{versus the alternative} \\ \mathbf{H}_a: p_{AVXS-101} &> 0.1\%, \end{aligned}$$

where  $p$  is the proportion of functional independent sitting for at least 30 seconds at the 18 months of age study visit.

The second co-primary efficacy hypothesis to be tested is:

$$\begin{aligned} \mathbf{H}_0: p_{AVXS-101} &= p_{HISTORICAL-FINKEL} \\ &\textit{versus the alternative} \\ \mathbf{H}_a: p_{AVXS-101} &\neq p_{HISTORICAL-FINKEL}, \end{aligned}$$

where  $p$  is the proportion surviving at 14 months of age.

Primary efficacy endpoints will be examined on the ITT population. Testing for the first co-primary endpoint, functional independent sitting will first be performed using 1-sided exact binomial test. Only if the null hypothesis of equality in proportion of functional independent sitting is rejected at  $p < 0.025$ , will the co-primary endpoint survival improvement be tested using 2-sided Fisher's Exact test on the ITT population, comparing to matched patients from natural observational study (PNCR). This hierarchy approach strongly protects the Type I error rate.

The hypothesis for both co-secondary efficacy endpoints to be tested is:

$$\begin{aligned} \mathbf{H}_0: p_{AVXS-101} &= 0.1\% \\ &\textit{versus the alternative} \\ \mathbf{H}_a: p_{AVXS-101} &> 0.1\%, \end{aligned}$$

where  $p$  is the proportion of patients maintaining the ability to thrive/are independent of ventilatory support.

One-sided exact binomial tests will be executed for secondary efficacy analyses on the ITT population.

A sensitivity analysis will be conducted by repeating the primary efficacy analysis on the efficacy completers analysis population.

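### The fixed testing sequence ends at the two co-primaries, leaving two formal co-secondary superiority tests with no gate, order or stated level

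*Protocol*

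**What the plan says.** Section 14.3.2 of the protocol covers the primary and secondary analyses together, on the ITT population, and gives them one purpose, superiority to the PNCR natural history study. It then writes out null and alternative hypotheses for four endpoints.

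- **Sitting** (first co-primary): one-sided exact binomial test against 0.1%, rejected at p < 0.025.
- **Survival** (second co-primary): two-sided Fisher's exact test against matched PNCR patients, done only if sitting is rejected. Section 14.2 puts the rule as "The 2 co-primary efficacy endpoints will be assessed in sequence" and gives two-sided 0.05 as the level.
- **Ability to thrive** and **ventilatory independence** (co-secondaries): each against 0.1%. The instruction is "One-sided exact binomial tests will be executed for secondary efficacy analyses on the ITT population".

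Between the co-primary and co-secondary hypotheses stands the sentence "This hierarchy approach strongly protects the Type I error rate".

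The co-secondary instruction carries no condition on the co-primaries, no order, no significance level and no adjustment. Nor does it call these analyses exploratory or descriptive, although section 14.1.2.3 does use the word descriptive for the All Enrolled population.

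**The concern.** A fixed sequence controls the error rate only for the tests inside it. Here two of the four formal superiority tests are outside. Followed literally, the trial could fail on sitting, never test survival, and still reject a pre-specified superiority null on thriving or ventilatory independence. It could also pass sitting, fail survival, and do the same. At stake is what the trial may claim after a partial failure, and whether a reader who meets the Type I error sentence in a section about primary and secondary analyses takes it to cover the secondary claims as well.

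**Working it through.** **Inputs.** Sections 14.2 and 14.3.2 give 15 ITT patients, about 30% excluded (leaving 10 or 11), null rate 0.1% for sitting and both co-secondaries, 26 controls with 25% survival, 80% survival on treatment, and 30% to 40% sitting. Two inputs are assumed because the protocol gives neither: one-sided 0.025 for each co-secondary test, and the correlation between tests.

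**The plan's own power figures first.** One sitter is enough to reject, so power for sitting is 1 − (1 − p)^n:
- n = 10, p = 30%: 1 − 0.7^10 = 0.972
- n = 11, p = 40%: 1 − 0.6^11 = 0.996

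The stated power above 90% holds. Full enumeration of the two-sided Fisher test, 80% against 25% with 26 controls, gives 0.819 (n = 10), 0.859 (n = 11) and 0.926 (n = 15). The stated power above 80% also holds.

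**Attained size of one test against 0.1%.** The test rejects at one or more successes, so the size is 1 − 0.999^n: 0.00996 (n = 10), 0.0109 (n = 11), 0.0149 (n = 15).

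The last figure is also the p-value for one success in 15. So with 0 of 15 sitting and 1 of 15 thriving, sitting fails, survival is not tested, and the thriving null is still rejected at 0.0149 < 0.025.

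**Global null: no effect on any endpoint.** Three tests can give a false claim: sitting and the two co-secondaries. Survival is behind the sitting gate, so it adds nothing. For independent tests the rate is 1 − (1 − a)^3, with a the attained size. For n = 15 this is 1 − (1 − 0.0149)^3 = 0.0440. For correlated tests, the three test statistics are taken as trivariate normal with equal correlation.

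| Patients analysed | Correlation 0 | 0.5 | 0.8 |
|---|---|---|---|
| 15 | 0.0440 | 0.0386 | 0.0304 |
| 11 | 0.0325 | 0.0289 | 0.0228 |
| 10 | 0.0296 | 0.0264 | 0.0208 |

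**Sitting truly effective, survival and both co-secondaries null.** At a common survival rate of 25%, the Fisher test's size in the benefit direction is 0.0166 (n = 10), 0.0167 (n = 11) and 0.0135 (n = 15). Combined with the two co-secondary tests:

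| Patients analysed | Correlation 0 | 0.5 | 0.8 |
|---|---|---|---|
| 15 | 0.0427 | 0.0375 | 0.0295 |
| 11 | 0.0381 | 0.0338 | 0.0268 |
| 10 | 0.0360 | 0.0320 | 0.0255 |

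**How far the result depends on the correlation model.** Suppose instead that the three binary outcomes are correlated within each patient through a beta-binomial model. At correlation 0.5 the chance that a null patient succeeds on at least one of three endpoints is 1 − (0.999 × 1.999 × 2.999)/6 = 0.00183. The global-null rate is then 1 − (1 − 0.00183)^n, or 0.027 (n = 15) and 0.018 (n = 10). At correlation 0.8 it is 0.0195 and 0.013.

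**With the sequence extended.** If each endpoint is tested only after the previous one succeeds, at one-sided 0.025 (two-sided 0.05 for survival), the chance of any false claim of benefit is at most 0.025, whatever the correlation.

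**The case against.** **The Type I error sentence is not wrong.** A reader might infer that the claim of strong protection is false. The text does not support that. The sentence closes the co-primary paragraph, directly after the sitting-then-survival rule and before any secondary hypothesis appears. For those two tests it is correct, and the co-primary conclusions are unaffected. What remains is a gap in coverage.

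**The co-secondaries may not be meant as confirmatory.** Section 14.3.1 frames the comparison with PNCR in terms of sitting and survival and says the other two endpoints will also be assessed. Level and power are given for the co-primaries only, and nothing says a co-secondary success can rescue a failed co-primary. This is fair, but 14.3.2 still puts the secondary analyses under the superiority aim with formal hypotheses. If they are descriptive, the protocol should say so.

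**The SAP may deal with it.** Section 14 calls itself a summary, and 14.2 sends the details of all analyses to the SAP. So the absence of a gate can be asserted only of the protocol. Yet the protocol did not leave multiplicity to the SAP: it fixed a hierarchy and then stated the secondary tests without condition. A gate in the SAP would have to override that sentence.

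**The inflation is small.** This stands. The benchmark of one-sided 0.025 is the plan's level for sitting; the plan states no family-wise level. With 10 or 11 patients and high correlation the global-null rate is below 0.025, and under patient-level correlation it can be below it at 15.

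**Conclusion.** The point holds as a gap in the protocol. Of four superiority tests in 14.3.2, two are sequenced and two are not, and a co-secondary claim could follow a failed co-primary. Under the global null, with one-sided 0.025 assumed for each co-secondary test and latent correlations of 0 to 0.8, the chance of at least one false claim is about 0.030 to 0.044 with 15 patients and 0.021 to 0.030 with 10.

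Two stronger conclusions are not supported. A reader might infer that the error rate simply exceeds 0.025; it does under some of these assumptions and not under others. A reader might also compute the rate as if every ungated test spent its full 0.025. Against the stated 0.1% null no test does so at these sample sizes, and such figures would need null rates the protocol does not use.

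The numerical inflation is modest. The main reason to act is that the protocol leaves open what may be claimed after a co-primary fails.

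**What to change.** In 14.3.2, replace the unconditional sentence on the secondary tests. State that the co-secondaries are tested only if both co-primaries are significant, in a pre-stated order, each at one-sided 0.025. Thriving and then ventilatory independence would follow the order in which the protocol lists them, though the sponsor should choose the order on priority. After the first failure, report the remaining endpoints as estimates with confidence intervals and make no superiority claim. Carry the same text into the SAP.

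Alternatively, label both co-secondary analyses descriptive and limit the Type I error sentence to the co-primaries.

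Either takes one or two sentences, with no added patients or data and no change to the co-primary tests or their power. The price of the first option is that a co-secondary claim is lost if an earlier step fails. At 30% sitting and 80% survival, both co-primaries succeed with probability at least 0.972 + 0.819 − 1 = 0.79 with 10 patients, and at least 0.995 + 0.926 − 1 = 0.92 with 15.

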#### **14.4. CHOP-INTEND Comparison**

A comparison will be performed of the first 3 patients CHOP-INTEND scores to the AVXS-101-CL-101 CHOP-INTEND scores. The first 3 patients enrolled must meet the criteria for the Intent-to-Treat (ITT) Population. AveXis will compare the CHOP-INTEND-1 month improvement for the AVXS-101-CL-303 patients that meet the ITT criteria to assess the clinical response to the dose  $1.1 \times 10^{14}$  vg/kg as being what was expected from the Cohort 2 patients in the Phase 1 trial (AVXS-101-CL-101). This comparison will be performed as a per patient assessment for the first 3 patients. The individual patients who receive their gene therapy at 0-3 months of age will be compared to a value of 10 CI points, while patients who receive their gene therapy at  $>3$  but  $<6$  months of age will be compared to a value of 5 CI points. Furthermore, patients from either age group are expected to maintain the improvement in the absence of an acute illness or perioperatively. If the expected CI improvements are observed for the first 3 ITT patients, AveXis will remove the 4-week interval between patients and proceed to dose at least

12 additional patients that meet the ITT criteria and perform safety and efficacy assessments as described elsewhere in the clinical protocol (AVXS-101-CL-303) and corresponding Statistical Analysis Plan. If the expected CI improvements are not observed for the first 3 ITT patients, AveXis will discuss next steps with the FDA before continuing study enrollment.

#### **14.5. Safety Analysis**

Safety will be assessed through the incidence and severity of AEs, vital sign assessments, cardiac assessments, laboratory evaluations (chemistry, hematology, urinalysis, immunology), physical examinations, and use of concomitant medications. Adverse events will be coded in accordance with the most current version of the MedDRA coding dictionary.

Safety analyses will be conducted on safety population and summarized by subgroup and overall.

## **15. DATA SAFETY MONITORING BOARD**

The DSMB is an independent multidisciplinary group consisting of clinicians and a biostatistician that, collectively, have experience in the management of patients with SMA Type 1 and other diseases, and in the conduct and monitoring of randomized clinical studies with interim analyses. The DSMB will be chartered to oversee the safety of patients during the conduct of the study and will act in an advisory capacity to AveXis. A detailed description of the DSMB, its role in this study, and the timing of the scheduled reviews will be described in a DSMB Charter.

The DSMB will routinely convene on a quarterly basis to review emerging safety data from the study. All available safety data from all enrolled patients will be included in such reviews, which include, but are not limited to, screen failures, enrollment status, data from safety parameters, all SAEs, and other AEs. Following each meeting, the DSMB will make a recommendation as to whether or not the accumulated safety data warrants a suspension or discontinuation of the study, a modification to the study, or any additional comments or recommendations related to safety. The DSMB will prepare and provide minutes of their meetings to AveXis who will provide copies to the regulatory authorities as appropriate.

The DSMB will also convene on an ad hoc basis within 48 hours should any patient experience an unanticipated CTCAE Grade 3 or higher AE/toxicity that is possibly, probably, or definitely related to gene replacement therapy, and is associated with clinical symptoms and/or requires medical treatment. This includes any patient death, important clinical laboratory finding, or any complication attributed to administration of gene replacement therapy. In such instances, the DSMB will review the safety information and provide its recommendation.

## **16. DIRECT ACCESS TO SOURCE DATA/DOCUMENTS**

### **16.1. Study Monitoring**

Before an investigational site can enter a patient into the study, a representative of AveXis will visit the investigational study site to:

- Determine the adequacy of the facilities
- Discuss with the Investigator(s) and other personnel their responsibilities with regard to protocol adherence, and the responsibilities of AveXis or its representatives. This will be documented in a Clinical Study Agreement between AveXis and the Investigator.

During the study, a monitor from AveXis or representative will have regular contacts with the investigational site, for the following:

- Provide information and support to the Investigator(s)
- Confirm that facilities remain acceptable
- Confirm that the investigational team is adhering to the protocol, that data are being accurately recorded in the case report forms, and that investigational product accountability checks are being performed
- Perform source data verification. This includes a comparison of the data in the case report forms with the patient's medical records at the hospital or practice, and other records relevant to the study. This will require direct access to all original records for each patient (e.g., clinic charts, electronic medical records)
- Record and report any protocol deviations not previously sent to AveXis
- Confirm AEs and SAEs have been properly documented on eCRFs and confirm any SAEs have been forwarded to AveXis and those SAEs that met criteria for reporting have been forwarded to the IRB/IEC.

The monitor will be available between visits if the Investigator(s) or other staff needs information or advice.

### **16.2. Audits and Inspections**

Authorized representatives of AveXis, a regulatory authority, an IEC or an IRB may visit the site to perform audits or inspections, including source data verification. The purpose of an AveXis audit or inspection is to systematically and independently examine all study-related activities and documents to determine whether these activities were conducted, and data were recorded, analyzed, and accurately reported according to the protocol, Good Clinical Practice (GCP) guidelines of the International Council for Harmonization (ICH), and any applicable regulatory requirements. The Investigator should contact AveXis immediately if contacted by a regulatory agency about an inspection.

### **16.3. Institutional Biosafety Committee**

As this study involves gene therapy, the Principal Investigator must obtain approval/favorable opinion for the investigation from a designated institutional or independent biosafety committee in accordance with institutional requirements and/or guidelines.

### **16.4. Institutional Review Board/Institutional Ethics Committee**

The Principal Investigator must obtain IRB/IEC approval for the investigation ([Section 18.1](#)). Initial IRB/IEC approval, and all materials approved by the IRB/IEC for this study including the patient consent form and recruitment materials must be maintained by the Investigator and made available for inspection.

## **17. QUALITY CONTROL AND QUALITY ASSURANCE**

Qualified individuals designated by the Sponsor will monitor all aspects of the study according to GCP, standard operating procedures (SOPs), and for compliance with applicable government regulations. Please see [Section 16.1](#) for more details regarding the quality control and monitoring process. AveXis may also conduct a quality assurance audit any time during or after the completion of the study. Please see [Section 16.2](#) for more details regarding the audit process.

The Investigator agrees to allow these Sponsor representatives direct access to the clinical data and supplies, dispensing and storage areas and if requested, agrees to cooperate fully or assist the Sponsor representative. The Investigator and staff are responsible for being present or available for consultation during routinely scheduled site visits conducted by the Sponsor or its designees.

Noncompliance with the protocol, ICH, GCP, or local regulatory requirements by an Investigator, site staff, or representatives of the Sponsor will lead to prompt action by the Sponsor to secure compliance. Continued noncompliance may result in termination of the corresponding party's involvement in the study. The IRB/IEC and relevant regulatory authority will also be informed.

## **18. ETHICS**

### **18.1. Ethics Review**

The final study protocol, including the final version of the Informed Consent Form, must be approved or given a favorable opinion in writing by an IRB or IEC, as appropriate. The Investigator must submit written approval to AveXis before he or she can enroll any patient into the study.

The Principal Investigator is responsible for informing the IRB or IEC of any amendment to the protocol in accordance with local requirements. In addition, the IRB or IEC must approve all advertising used to recruit patients for the study. The protocol must be re-approved by the IRB or IEC upon receipt of amendments and annually, as local regulations require.

The Principal Investigator is also responsible for providing the IRB or IEC with reports of any reportable serious adverse drug reactions from any other study conducted with the investigational product. AveXis or designee will provide this information to the Principal Investigator.

Progress reports and notifications of serious adverse drug reactions will be provided to the IRB or IEC according to local regulations and guidelines.

Initial IRB/IEC approval, and all materials approved by the IRB/IEC for this study including the patient consent form and recruitment materials must be maintained by the Investigator and made available for inspection.

### **18.2. Ethical Conduct of the Study**

The study will be performed in accordance with ethical principles that have their origin in the Declaration of Helsinki ([Appendix 6](#)) and are consistent with ICH/GCP, applicable regulatory requirements and the AveXis' policy on Bioethics.

### **18.3. Written Informed Consent**

The Principal Investigator(s) at each center will ensure that the parent(s)/legal guardian(s) are given full and adequate oral and written information about the nature, purpose, possible risk and benefit of the study. The parent(s)/legal guardian(s) must also be notified that they are free to discontinue the patient from the study at any time. The parent(s)/legal guardian(s) should be given the opportunity to ask questions and allowed time to consider the information provided.

The signed and dated informed consent must be obtained before conducting any study procedures.

The Principal Investigator(s) must maintain the original, signed Informed Consent Form. A copy of the signed Informed Consent Form must be given to the parent(s)/legal guardian(s).

There will be 3 informed consent forms:

- Parent(s)/legal guardian(s) informed consent form
- Biological mother baseline AAV9 antibody screening informed consent form

- Autopsy informed consent form ([Appendix 1](#); if the parent(s)/legal guardian(s) decline an autopsy, it will not prevent the patient from participating in the study)

## **19. DATA HANDLING AND RECORDKEEPING**

### **19.1. Electronic Case Report Forms**

Adequate and accurate case records will be maintained, and all relevant observations and data related to the study will be recorded. This will include medical history/ physical examination, hematology, clinical chemistry and serology results, a check list of inclusion and exclusion criteria, product administration, and a record of sample collection, hemodynamic measurements, clinical assessments, AEs, and final evaluation.

Electronic CRFs will be used in this study. The eCRF will be electronically signed and dated by the Principal Investigator or designee after his/her review. After the completion of the study, completed eCRFs will be retained in the archives.

Completed eCRFs will be reviewed by the study monitor against the source documentation for accuracy and completeness. Once signed by the Investigator, the monitor will transmit the completed eCRFs to data management for data validation and database analysis.

